7. STATISTICAL ANALYSIS

7.1 Subject screening, disposition and protocol deviations

The screening failure subjects and the reasons for screening failure will be summarized by the numbers and percentages. The percentages are based on the number of screening failure subjects.

The disposition of subjects will be summarized, including the numbers and percentages of subjects for the following categories: all enrolled subjects, subjects completed the study, subjects early discontinued from the study, subjects in the modified intent to treat population, subjects in the perprotocol population, and subjects in the safety analysis population. All percentages are based on the number of all enrolled subjects.

The primary reason for subject premature discontinuation from study will also be summarized. The reasons for discontinuation will include voluntarily discontinue participation, lost to follow-up, lack of efficacy, subjects with treatment interruptions of ≥ 28 consecutive days, adverse event, intercurrent illness, protocol violations, pregnancy, and other reason. A listing will be provided.

Protocol deviations will be summarized and listed for mITT population. Subject counts and percentages will be displayed by the following deviation categories:

- Poor compliance, defined as taking < 80% or > 120% of the required number of tablets
- Take the prohibited medication specified in protocol during the treatment period
- With actual visit day being more than 14 days deviated from the schedule visit day
- · Had other significant protocol violations that were thought to affect the efficacy evaluation

Major protocol deviations which results in the exclusion of the subject from PP population will be discussed, determined, and documented by study team before final database lock.

7.2 Subject Information

7.2.1 Demographics and baseline characteristics

Demographic and baseline characteristics for subjects include subject age, sex (Male/Female), race (Asian/Others), weight, height, BMI, systolic blood pressure, diastolic blood pressure, pulse, respiratory, body temperature, alcohol abuse, drug abuse, history of medication hypersensitivity, cirrhosis and resistance mutations. Percentages for categorical data will be calculated based on the number of subjects in the analysis set of that treatment group. Descriptive statistics will be used for continuous data. A listing of demographics and baseline characteristics will also be provided. Age will be calculated by

Age (Year) = Year of Informed Consent Date - Year of Birth + 1

7.2.2 Medical history

Medical history will include any acute and chronic medical conditions including prior surgery, information related to hepatitis B history, any current and prior HBV medications, and previous HBV-related procedures.

Medical history will be listed by system organ class and preferred term coded in MedDRA 17.0.

The previous treatment of chronic hepatitis B will also be summarized by drug categories (LAM, LdT, ETV, ADV, IFN) with drug duration >6 months. Drugs with duration \leq 6 months will not be counted.

7.2.3 Inclusion and exclusion criteria

Subjects must meet all specified inclusion and none of the exclusion criteria in order to be eligible to participate in the study. Inclusion and exclusion criteria information will be presented in the listing.

7.3 Treatments and medications

7.3.1 Prior and concomitant medication

Prior medication: all the drugs taken by the subjects prior to the first dose date of TDF.

Concomitant medication: all the drugs taken by the subjects from the first dose date of TDF to completion of the study.

If medication start date is on or after the first dose date of TDF, then medication will be summarized as concomitant medication regardless of whether medication end date is missing or not. If medication end date is before the first dose date of TDF, then medication will be summarized as prior medication regardless of whether medication start date is missing or not. Note that medication that started prior to the first dose date of TDF and continued after dosing will be summarized as prior medication and separately as concomitant medication.

All medications will be coded according to WHO drug dictionary (Version: WHODDE 2016Q3) and Anatomical Therapeutic Chemical (ATC) coding.

Medication class, medication name, indications, total daily dose, unit, route, start date and end date will be presented in the listing.

7.3.2 Non-drug therapies

For subjects who receive any non-drug therapy will be recorded on eCRF. Non-drug therapy information including therapy details, start and end date, and the reason for use will be presented in the listing.

7.3.3 Treatment compliance

The duration in days of study drug exposure from first dose date to the last dose date will be summarized by descriptive statistics.

The duration of the drug exposure (day) = Last dose date - First dose date + 1

Treatment compliance, defined as actual taken amount divided by expected taken amount per protocol times 100, will be summarized by descriptive statistics for mITT. The formulas for calculating the treatment compliance are as follows:

Treatment Compliance (%) = Actual taken amount×100 / Expected taken amount

Drug accountability information including date (dispensed or returned), dispensed amount, returned amount, lost amount, expected taken amount, actual taken amount, missing amount, and treatment compliance will be presented in the listing.

7.4 Efficacy analysis

This analysis will be conducted in mITT and PP population.

7.4.1 Analysis of primary variable

The primary efficacy endpoint for this study is the proportion of subjects with serum HBV DNA <20 IU/mL at week 144. Primary efficacy endpoints are evaluated by count and percentage, and two-sided 95% CI will also be provided based on normal approximation and continuity correction.

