# 2. OBJECTIVE(S)

## 2.1. Primary Objective

• To assess the proportion of multiple NA treatment failure chronic hepatitis B patients that achieves HBV DNA<20 IU/mL at week 144 of TDF treatment

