- Subjects have HBV DNA ≥200IU/ml at week 48 and afterwards have ≤ 1 log10 IU/ml decrease in HBV DNA at two consecutive tests, confirmed by a third visit(additional visit) at least one month apart.

Meanwhile, subjects to be received rescue therapy must have investigational product (IP) compliance > 80% in the last regular visits period (usually 12 weeks).

Another NA(s) without cross-resistance (eg. LAM, LdT, or ETV) will be added, the choice to be decided by the investigator.

Additional Visit: During the treatment phase, subjects who do not achieve satisfied response to TDF (eg.experience virological breakthrough or HBV DNA level does not continue to decline,) need to perform another HBV DNA test at an additional visit at least one month apart. Before rescue treatment initiation, serum sample should be collected for resistance testing.

During the treatment phase, patients that have evidence of HBsAg loss or seroconversion and HBeAg loss/seroconversion (for baseline HBeAg positive subjects) and HBV DNA < 20 IU/ml at any two consecutive visits at least 3 months apart will enter a non-treatment observational arm of the study, and will be followed up until the end of the study according to protocol-defined assessments and procedures. Study treatment should be stopped within 15 days of the result confirming that the subject meets the criteria.

If a patient in the non-treatment observational arm subsequently develops HBV DNA  $\geq$ 20 IU/ml, HBsAg re-emerges, and ALT > 1.5 ULN, they will be eligible to be re-treated with TDF up to week 144 of the study. Once the treatment is restarted, the patients should be followed at least every 12 weeks as protocol defined and the data will be entered as the corresponding scheduled visit.

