# 5. STUDY TREATMENTS

## 5.1. Investigational Product and Other Study Treatment

Tenofovir disoproxil fumarate (9-[(R)-2-[[bis[[(isopropoxy-carbonyl) oxy] methoxy] phosphinyl] methoxy] propyl] adenine fumarate (1:1)); GS4331-05) is an oral pro-drug

(bisPOC-PMPA) of TFV (PMPA), an acyclic nucleoside phosphonate (nucleotide) analogue of adenosine 5'-monophosphate. TDF has demonstrated antiviral activity against HBV and HIV and is indicated for use in combination with other antiretroviral agents in the treatment of HIV infection.

Tenofovir disoproxil fumarate tablets are white, almond-shaped, film-coated tablets containing 300 mg of TDF, debossed with "GILEAD" and "4331" on one side of the tablet. Each tablet contains the following inactive ingredients: microcrystalline cellulose, lactose monohydrate, pregelatinised starch, croscarmellose sodium, and magnesium stearate. The tablets are film coated with Opadry II White 32K18425.

TDF are packaged in white, high-density polyethylene bottles with a white child resistant cap. There are 30 tablets per bottle. Each bottle also contains silica gel canister(s) to protect the product from humidity and fibre packing to protect the product during handling and shipping.

For subjects who do not achieve satisfied response to TDF will add another drug without cross resistant to TDF including LAM (Heptodin, GlaxoSmithKline, 100mg QD), ETV (Baraclude, Bristol-Myers Squibb,0.5mg QD) and LdT(Sebivo,Novartis,600mg QD). Investigator will make the decision for the drug selection.

The contents of the label will be in accordance with all applicable regulatory requirements.

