## 8.3.5. Key Elements of Analysis Plan

Missing data can have an impact upon the interpretation of the trial data. In general, values for missing data will not be imputed unless otherwise specified.

All serum HBV DNA results below the lower limit of detection will be analysed as being the value of the lower limit of detection.

For the primary analysis of HBV DNA<20IU /ml at Week 144, data from non-completers will be considered to be "failures".

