6.2 Data handling

Missing data can have an impact upon the interpretation of the trial data. In general, values for missing data will not be imputed unless otherwise specified.

All serum HBV DNA results below the lower limit of detection (<20 IU/mL) or results of "not detected" will be analyzed as being the value of the lower limit of quantification, which is 20 IU/mL. For the primary endpoint analyses and other analyses of response (success, failure) at a particular time point, a discontinued subject was considered as "failure" for all efficacy responses post termination. And the missing values of categorical efficacy endpoints (success, failure) will be imputed as "failure" at the analysis visits.

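### A subject given an add-on NA after failing TDF counts as a success if below 20 IU/mL at week 144, and no listed output gives the response rate with rescued subjects as failures

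*SAP*

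**What the plan says.** **Objective and endpoint.** Protocol 2.1 asks what proportion of subjects "achieves HBV DNA<20 IU/mL at week 144 of TDF treatment". SAP 7.4.1 makes this operational: "The primary efficacy endpoint for this study is the proportion of subjects with serum HBV DNA <20 IU/mL at week 144". Neither mentions add-on treatment.

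**Rescue.** Protocol 3.1 has two triggers. One is a confirmed rise of at least 1 log10 above nadir. The other is HBV DNA of at least 200 IU/mL at week 48, followed by no more than a 1 log10 "decrease in HBV DNA at two consecutive tests, confirmed by a third visit(additional visit) at least one month apart". When a trigger is met, "Another NA(s) without cross-resistance (eg. LAM, LdT, or ETV) will be added, the choice to be decided by the investigator". Protocol 5.1 repeats this: "For subjects who do not achieve satisfied response to TDF will add another drug without cross resistant to TDF". There is a further condition: "subjects to be received rescue therapy must have investigational product (IP) compliance > 80% in the last regular visits period". Rescue is not among the withdrawal criteria in Protocol 4.4, so the subject continues on TDF plus the added drug.

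**Failures.** Under Protocol 8.3.5, "data from non-completers will be considered to be" failures. SAP 6.2 scores a discontinued subject as a failure "for all efficacy responses post termination. And the missing values of categorical efficacy endpoints (success, failure) will be imputed as" failure. Rescue does not appear in either rule.

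**Related outputs already planned.** SAP 7.4.2 gives the incidence of viral breakthrough and of unsatisfactory response, overall and by visit, with 95% CIs (Tables 4.7.3, 4.7.4, 4.8.1 and 4.8.2). Listings 4.1.2 and 4.1.3 show HBV DNA for those subjects.

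**The concern.** The study is meant to show how well TDF works after several NAs have failed, and in particular whether resistance mutations weaken the response. A subject who has failed on TDF, receives a second drug and is then suppressed appears in the results as a TDF responder. The same virological failure is scored as a failure if the subject discontinues for lack of efficacy.

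The secondary and exploratory results are the most exposed: response rates in the multi-drug-resistance subgroup, the week-144 logistic model of baseline factors, and time to response, which SAP 5.3 and 7.4.3 describe as response to TDF. If rescue is commoner in subjects with resistance, as-observed scoring lifts their rate more than that of the others and narrows the contrast that the study wants to measure.

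**Working it through.** **How the rules classify a rescued subject.** Take a subject who meets a trigger, has an NA added, attends week 144 and has HBV DNA below 20 IU/mL.

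- Non-completer (Protocol 8.3.5)? No.
- Discontinued (SAP 6.2)? No, because the drug is added on study.
- Missing value (SAP 6.2)? No.
- Below 20 IU/mL (SAP 7.4.1)? Yes, so a success in mITT.
- Removed from PP? Apparently not. Protocol 5.6.2 exempts drugs that the protocol allows, and SAP 7.1 lists only prohibited medication as a deviation.

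In the time-to-response analysis, a subject who had not been below 20 IU/mL before add-on and reaches it afterwards is an event.

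**Which visits are exposed.** The unsatisfactory-response route cannot act before about week 60 + 4 = 64 (if week 48 is the first of the two tests) or week 72 + 4 = 76 (if they are weeks 60 and 72). Week 144 is mainly affected and week 96 less. Week 48 is exposed only through early confirmed breakthrough.

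**The plan's own precision figure.** From Protocol 8.2.1, p = 0.80 and E = 0.06, with z = 1.96:

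- N = 0.80 × 0.20 × (1.96/0.06)² = 170.7, against 170 stated; 170/0.85 = 200. Both reproduce.
- Half-width at n = 200 with the SAP's continuity correction: 1.96 × √(0.16/200) + 1/400 = 5.79 points.

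**Gap between the two scorings.** Let r be the share rescued and q the share of those below 20 IU/mL at week 144. Then gap = r × q.

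- One rescued responder: 1/200 = 0.5 point overall.
- Protocol 1.2 expects up to 20% with multi-drug resistance: 0.20 × 200 = 40 subjects, so 1/40 = 2.5 points each.
- Twelve rescued responders: 12/200 = 6.0 points, just over the 5.79-point half-width.

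The documents give neither r nor q. Under assumed r of 2–15% and q of 30–70%:

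- low: 2% × 30% = 0.6 point
- middle: 5% × 50% = 2.5 points
- high: 15% × 70% = 10.5 points

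**Net of what TDF alone would have achieved.** The part due to the second drug is r × (q − q0), where q0 is the share of rescued subjects who would have been suppressed without it. The prospective study in Protocol 1.2 had 27/59 suppressed at week 48 and 38/59 at week 96, so a net (38 − 27)/(59 − 27) = 11/32 = 34.4% of those not suppressed at week 48. With q0 = 34.4%:

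- middle: 5% × (50% − 34.4%) = 0.8 point
- high: 15% × (70% − 34.4%) = 5.3 points
- zero where q does not exceed q0

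Some subjects in that study also took LAM, and they were not selected for lack of decline, so q0 is probably lower here. It need not be near zero: a fall from 200 to 21 IU/mL is log10(200/21) = 0.98, which still meets the trigger.

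**What the planned tables supply.** The breakthrough and unsatisfactory-response tables approximate a ceiling on r. They do not count rescue given, which also needs compliance above 80%, and no listed title crosses them with week-144 response.

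**The case against.** The strongest reply is that nothing in the primary analysis is ambiguous. The rules give one classification, the study is descriptive with no hypothesis, and a rescued subject is still taking TDF. That stands. A reader might infer that the primary endpoint is mis-scored, or that rescue-as-failure should be the headline. The documents support neither. The objective in Protocol 2.1 refers to week 144 of TDF treatment and does not say TDF alone. Rescue-as-failure also has a bias of its own: because rescue requires compliance above 80%, a compliant rescued subject fails while a less compliant, unrescued subject with the same virology can still succeed.

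A reader might also say that the logistic model credits the second drug's effect to TDF. It cannot: every subject receives TDF and the model has no TDF term. What can change is the association between baseline factors and response.

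It is also fair that the SAP already reports both trigger events and lists HBV DNA for those subjects, so someone with the listings could approximate the stricter rate. But triggers are not the same as rescue given, and an approximation made afterwards is not a planned analysis. Mock tables are in a separate document, so the absence can be judged only from the listed titles.

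**Conclusion.** The point holds as a gap in the supporting analyses, not as an error in the primary one. Followed exactly, the plan counts responses reached on TDF plus a second NA as responses in the resistance subgroups and the baseline-factor model, and as events in time to response to TDF. No listed output shows the alternative.

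The size is unknown. The firm figures are 0.5 point per rescued responder of 200 and about 2.5 points in a subgroup of about 40. The 0.6 to 10.5 point range rests on assumed r and q, and its upper end has no direct support in the documents. It is also an upper bound on the second drug's contribution: the middle case net of q0 is 0.8 point. A reader should not infer that the headline rate is materially inflated. If rescue is rare the effect is small. That resistance contrasts would narrow is likewise conditional on rescue being commoner in resistant subjects.

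**What to change.** Keep the as-observed primary analysis. Before database lock, add to SAP 7.4:

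1. A supplementary analysis of the <20 IU/mL response rate, overall and in the resistance subgroups, and of the week-144 logistic model, counting subjects as failures at visits after an add-on NA starts.
2. In the time-to-response analysis, a rule that a first value below 20 IU/mL reached after add-on is not an event.
3. A table of the number rescued, overall and by mutation pattern.

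Show the supplementary results beside the as-observed ones, with a note on the compliance condition, since each scoring has its own bias.

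The cost is a few sentences and one or two tables. Add-on start dates are already in the concomitant-medication data (SAP 7.3.1). The supplementary rate may be lower than the primary one. Sample size, rescue criteria and rescue treatment do not change.

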7.4.2 Analysis of secondary variables

Analysis for secondary variable of the log₁₀ reduction in serum HBV DNA by patterns of mutation and overall per visit will be summarized by descriptive statistics as the mean, standard deviation, two-sided 95%CI, minimum, median, maximum, and the number of observations. The patterns of mutation will be summarized by 2 categories. One includes wild-type, LAM-R, ADV-R and ETV-R. The other one includes wild-type, ADV-R single mutation (A181T/V; N236T), ADV-R double mutation (A181T/V+N236T)) and other mutation. Nominal P values between different patterns of mutation will be provided at week 24, 48, 96, 144. Individual HBV DNA levels of subjects with genotypic resistance to ADV (A181T/V+N236T) will be summarized over time by figure.

In addition, the number and percentage will be presented respectively for secondary variables including:

- The proportion of subjects with virological response (serum HBV DNA <20 IU/mL and serum HBV DNA <69 IU/mL, separately) by visit
- The proportion of subjects with virological response (serum HBV DNA <20 IU/mL and serum HBV DNA <69 IU/mL, separately) by visit in the subgroup with confirmed multi-drug resistance at baseline
- The proportion of subjects with virological response(serum HBV DNA <20 IU/mL and serum HBV DNA <69 IU/mL, separately) by visit in the subgroup with medical history (previously exposed to ADV >6 months or not, ETV >6 months or not) (Subjects with ETV >6 months will be separated as ETV-R and non ETV-R)
- The proportion of subjects achieving HBeAg loss, HBeAg seroconversion, HBsAg loss and

HBsAg seroconversion at Week 48, 96 and 144 for HBeAg positive subjects

- The proportion of subjects achieving HBsAg loss and HBsAg seroconversion at Week 48, 96 and 144 for HBeAg negative subjects
- The proportion of subjects with ALT normalization at week 48, 96 and 144 in subjects who have abnormal ALT at baseline
- The incidence of subjects who experience viral breakthrough (defined as 1 log increase in HBV DNA from nadir determined by two sequential HBV DNA measurements) overall and by each visit.
- The proportion of subject with unsatisfactory response, overall and by each visit. Unsatisfactory response is defined as subjects who have HBV DNA ≥200 IU/mL at week 48 and afterwards have ≤1 log10 IU/mL decrease in HBV DNA at two consecutive tests, confirmed by a third visit (additional visit) at least one month apart
- Mutation pattern change from baseline at week 48, 96, 144

Also, two-sided 95% CI will be calculated for each percentage.

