## 4.2. Inclusion Criteria

Specific information regarding warnings, precautions, contraindications, adverse events, and other pertinent information on the GSK investigational product or other study treatment that may impact subject eligibility is provided in the IB/IB supplement(s).

Deviations from inclusion criteria are not allowed because they can potentially jeopardise the scientific integrity of the study, regulatory acceptability or subject safety. Therefore, adherence to the criteria as specified in the protocol is essential. Subjects eligible for enrolment in the study must meet all of the following criterion:

- 1. Aged between 18–65 years (inclusive).
- 2. Male or female; a female is eligible to enter and participate in this study if she is of:
  - a. Non-childbearing potential (i.e., physiologically incapable of becoming pregnant, including any female who is post-menopausal); or,
  - b. Child-bearing potential, has a negative urine pregnancy test at baseline, and agrees to one of the following methods for avoidance of pregnancy during the period of the study and until 30 days after last dose of study medication:
    - Oral contraceptive, either combined or progestogen alone.
    - Injectable progestogen.
    - Implants of levonorgestrel.
    - Oestrogenic vaginal ring.
    - Percutaneous contraceptive patches.
    - Intrauterine device (IUD) or intrauterine system (IUS) showing that the expected failure rate is less than 1% per year as stated in the IUD or IUS product label.
    - Has a male partner who is sterilised.
    - Double barrier method: condom and an occlusive cap (diaphragm or cervical/vault caps) with a vaginal spermicidal agent (foam/gel/film /cream/suppository).
- 3. The ability to understand and sign a written informed consent prior to any studyrelated procedure and comply with the requirements of the study.
- 4. Positive HBsAg for more than 6 months, and anti-HBs negative.
- 5. Serum HBV DNA level  $\geq 200$  IU/ml at study screening (Use central lab results).
- 6. Experienced multiple NAs treatment failure which is defined as HBV DNA higher than 200 IU/ml after two or more different NA(s) treatments (i.e. initiate with mono-therapy, followed by add-on/switch rescue therapy; at least 6 months continuous treatment for each regimen, total duration to be no less than 12 months). In addition, subjects judged by the treating physician to have adhered to previous NA therapy.

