#### 201215

- 1 All results to be obtained before baseline visit.
- 2 No more than 6 days before or 6 days after the date scheduled based on the time from baseline visit not from the previous visit.
- 3 Demographic data includes birth date, gender and race
- 4 Medical history will include any acute and chronic medical conditions including prior surgery, information related to hepatitis B history, any current and prior HBV medications, and previous HBV-related procedures.
- 5 Update any new medical conditions and/or concomitant medications that have occurred since study screening.
- 6 Concomitant medications including traditional Chinese medicines and/or herbal remedies.
- 7 At screening, a complete physical examination will be performed. For all following indicated visits, a brief physical examination will be performed.
- 8 Including blood pressure, pulse, respiratory rate and temperature.
- 9 Urine pregnancy test will be performed at screening, baseline and every 3 months after dosing.
- 10 Tests will be performed at central lab.
- 11 B ultrasound examination include liver, pancreas, spleen, gall bladder and kidney.
- 12 Urinalysis: urine glucose, ketones, specific gravity, blood, pH and protein.
- 13 HBV DNA will be tested using Roche COBAS Taqman HBV test (LLD:20IU/ML).
- 14 Resistance surveillance will be performed at baseline or under the condition defined in protocol by direct sequencing of the polymerase gene. See Section 6.2.5
- 15 Each study visit: All study medication to be collected and reconciled.

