3.2 Sample size

Sample sizes are chosen based on feasibility and precision because no hypothesis is tested in this study. The primary endpoint is the proportion of subjects with serum HBV DNA <20 IU/mL of TDF in multiple NAs treatment failure patients at Week 144.

To decide the number of subjects for analysis, some precision calculations have been performed. From our historical data, we hypothesize that the proportion of subjects with serum HBV DNA <20 IU/mL in multiple NAs treatment failure patients treated with TDF at Week 144 was 80%. A sample size of 170 patients will allow us to estimate the confidence interval of the incidence with a margin of error at 6% (range from 74-86%). Assuming a dropout rate of 15 per cent during a 144 week period, the number of patients required overall is estimated to be 200.

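### Setting HBV DNA below 20 IU/mL to 20 makes the mean log10 reductions lower bounds and distorts the comparisons between mutation patterns; their confidence intervals and P values do not allow for this

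*SAP*

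**What the plan says.** Footnote 13 to Table 1 of the protocol states the assay and its limit: "HBV DNA will be tested using Roche COBAS Taqman HBV test (LLD:20IU/ML". Under SAP 6.2, any result below 20 IU/mL or reported as not detected "will be analyzed as being the value of the lower limit of quantification, which is 20 IU/mL". Protocol 8.3.5 has the same rule: "All serum HBV DNA results below the lower limit of detection will be analysed as being the value of the lower limit of detection".

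SAP 7.4.2 then says that the log10 "reduction in serum HBV DNA by patterns of mutation and overall per visit will be summarized by descriptive statistics as the mean", with SD, two-sided 95% CI, median and range. It adds nominal P values between mutation patterns at weeks 24, 48, 96 and 144, without naming a test. The log10 reduction at weeks 48, 96 and 144 is a listed secondary endpoint (SAP 5.2). Most of the related tables (4.7.1 to 4.7.2.2) are marked for the annual outputs, which SAP 3.1 says serve publication.

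On how many subjects will be at the limit, the plan gives one expectation. SAP 3.2 takes the proportion below 20 IU/mL in patients "treated with TDF at Week 144 was 80" per cent. Neither document mentions a method for censored data or says that the mean reduction is a lower bound.

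**The concern.** A result below 20 IU/mL tells us only that the value lies somewhere under log10(20) = 1.30. Once 20 is substituted, that subject's reduction is baseline log10 minus 1.30, whether the true level is just under the limit or far below it. The mean, SD, CI and P values treat this figure as a measurement.

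Three consequences follow. The mean reduction is biased low. The bias grows as more subjects reach the limit, so the apparent gain from week 48 to week 144 is flattened. Comparisons between mutation patterns become partly comparisons of how many subjects reached the limit and where each group started. At stake is what a named secondary endpoint, and its annual outputs, can be taken to show.

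**Working it through.** **The plan's own figure.** With p = 0.80, e = 0.06 and z = 1.96, N = p(1−p)(z/e)² = 0.16 × (1.96/0.06)² = 170.7, against 170 stated; 170/0.85 = 200. The half-width at n = 170 is 1.96 × √(0.16/170) = 6.01%, which agrees with "with a margin of error at 6% (range from 74-86" per cent. So 0.80 × 170 = 136 of 170 evaluable subjects are expected at the substituted value at week 144.

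**Ceiling per subject.** The largest reduction a subject can show is log10(baseline) − log10(20): 1.0 at 200 IU/mL (the screening minimum in protocol 4.2), 3.0 at 20,000 and 5.0 at 2,000,000.

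**Understatement of the mean.** Assume latent log10 HBV DNA is normal with standard deviation SD, and let p be the share below the limit. With d = Φ⁻¹(p), the understatement is SD × [d·p + φ(d)]. The 80% is the plan's figure. The 46% and 64% come from a cited prospective study of 59 patients (protocol 1.2) that used <15 IU/mL and included some patients on TDF plus LAM. They are a guide, not an assumption of this plan. The SDs are assumed.

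| Week | p | d | φ(d) | SD 0.5 | SD 1.0 | SD 1.5 |
|---|---|---|---|---|---|---|
| 48 | 0.46 | −0.100 | 0.397 | 0.18 | 0.35 | 0.53 |
| 96 | 0.64 | 0.358 | 0.374 | 0.30 | 0.60 | 0.91 |
| 144 | 0.80 | 0.842 | 0.280 | 0.48 | 0.95 | 1.43 |

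For week 144 at SD 1.0: 0.842 × 0.80 + 0.280 = 0.95.

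**Does the CI allow for it?** In a simulation (assumed baseline mean 5 and SD 1 log10, floored at 200 IU/mL; reduction SD 1):

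| True mean reduction | Share at limit | Reported mean | CI half-width, n = 200 |
|---|---|---|---|
| 2.0 | 11% | 1.92 | 0.13 |
| 3.0 | 31% | 2.72 | 0.12 |
| 3.6 | 47% | 3.08 | 0.11 |
| 4.2 | 64% | 3.35 | 0.12 |
| 5.0 | 82% | 3.56 | 0.12 |

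From 31% at the limit onward, an interval centred on the expected reported mean excludes the true mean. The median is no remedy: at 82% it is 3.59 against a true 5.0.

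**Differences between patterns, equal baselines.** A true difference in reduction of 1.0 log10 is reported as 0.80 with 31% and 11% at the limit, 0.29 with 82% and 58%, and 0.19 with 90% and 71%.

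**Differences between patterns, unequal baselines** (all SDs 1):

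| Baseline means, A and B | True difference A − B | Reported difference |
|---|---|---|
| 4 and 5 | 0 | −0.88 |
| 4 and 5 | +0.5 | −0.76 |
| 5 and 6 | −0.5 | −0.88 |

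So a difference can be created, reversed or enlarged.

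**The case against.** The rule is prespecified and common, the study tests no hypothesis, the P values are called nominal, and understating the drug's effect is conservative. The rationale asks how ADV resistance affects response rates, not mean decline. That question has analyses which do not depend on the value assumed below 20: proportions <20 and <69 IU/mL by visit, including by multi-drug resistance and by ADV or ETV exposure (SAP 7.4.2), and logistic regression on resistance type plus Kaplan-Meier, log-rank and Cox analyses (SAP 7.4.3). The overall share below 20 is already in Tables 4.2.1 and 4.2.2. Much of this stands and limits the point to a secondary endpoint. It does not repair that endpoint: a 95% CI and between-group P values are inferential, and nothing beside the means tells the reader how many values are at the limit.

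A reader might go further in three ways that the documents do not support.

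- Most values are below the limit throughout. The plan supports this only at week 144. The one week 48 figure is 46%, from another study, and there is none for week 24.
- Substitution always pulls pattern differences towards zero and so hides an ADV-resistance effect. That needs equal baselines, and protocol 1.2 itself offers differing baseline titre as the possible reason two studies disagreed. The 52% response quoted there for ADV resistance is at <400 copies/ml, so it cannot be used as a share below 20 IU/mL.
- A censored (Tobit) model should replace the means. It recovers the truth when data are normal, but it can be worse otherwise. Take an assumed two-cluster shape with 90% and 52% suppressed, suppressed subjects grouped between 0 and 1.0 log10, and the rest around 3 (SD 0.8). The true difference was then 0.77 to 1.15; substitution gave about 0.65 and the censored model about 2.6. Such a shape is plausible where non-responders form a distinct group. A fully suppressed pattern has no finite estimate.

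**Conclusion.** The point holds for the continuous log10 reduction endpoint. That the substituted mean is a lower bound is arithmetic and needs no distributional assumption. Its size does: about 0.95 log10 at week 144 for SD 1.0 (0.48 to 1.43 for SD 0.5 to 1.5), given the plan's 80% and a normal latent distribution. The documents cannot settle the size, because values below 20 are unknown and no on-treatment SD is given. The planned CI reflects sampling error only.

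For mutation patterns the defensible statement is that differences are distorted, in a direction that depends on baselines. The nominal P values carry the same distortion. The primary endpoint, the response proportions and the time-to-response analyses are unaffected, provided response is read from the laboratory result before substitution. This should be corrected, but it does not threaten the main conclusion of the trial.

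**What to change.** In SAP 7.4.2:

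1. Report mean log10 reductions as lower bounds ('at least'), with the number and percentage at the 20 IU/mL limit beside each mean, overall and by mutation pattern.
2. State that their 95% CIs and P values are not inference on true decline once a material share of subjects is at the limit.
3. Base pattern comparisons on the proportions <20 and <69 IU/mL and on time to response. The Kaplan-Meier figures already use both mutation groupings; the listed proportion tables do not, so that split has to be added.
4. Add, as a sensitivity analysis where estimable, a regression of log10 HBV DNA left-censored at log10(20) on mutation pattern and baseline log10 HBV DNA.
5. Keep weeks 48, 96 and 144 as the endpoint timepoints.

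The cost is SAP wording, some added columns and tables, and one standard procedure; no new data are needed. The censored model relies on a normal shape and can mislead if values are bimodal or a pattern is fully suppressed, so it should not be the sole source of inference.
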